## 8.2.3 Electrocardiograms

Standard 12-lead ECGs will be recorded at the times given in the SoA (Section 1.3) using an ECG machine that automatically calculates the heart rate and measures PR, QRS, QT, and corrected QT (QTc; according to Bazett) intervals.

ECGs will be judged by the investigator as clinically significant (yes/no); only the investigator assessment and heart rate will be recorded in the CRF.

# 8.2.4 Clinical laboratory tests

See Section 10.2 for the list of clinical laboratory tests to be performed at the times given in the SoA (Section 1.3).

The investigator must review the laboratory report, document this review with signature and date, and record any clinically relevant changes occurring during the trial in the AE section of the CRF. The laboratory reports must be filed with the source documents.

All laboratory tests with values considered clinically significantly abnormal during participation in the trial should be repeated until the values return to normal or baseline or are no longer considered clinically significant by the investigator or the sponsor's Medical Monitor.

If such values do not return to normal/baseline within a period of time judged reasonable by the investigator, the etiology should be identified and the sponsor notified.

All protocol-required clinical laboratory tests (see Section 10.2) must be conducted in accordance with the trial site standard.

If laboratory values from non-protocol-specified laboratory assessments performed at the laboratory require a change in trial subject management or are considered clinically significant by the investigator (e.g., SAE, AE or dose modification), then the results must be recorded in the CRF.

#### 8.2.5 Drugs of abuse screening

Screening for drugs of abuse (amphetamines, benzodiazepines, barbiturates, cocaine, cannabinoids, opiates, methadone, methamphetamines, phencyclidine, and tricyclic antidepressants) will be performed using a commercially available kit at the times given in the SoA (Section 1.3).

## 8.2.6 Testing for alcohol use

Breath testing for alcohol use will be performed at the times given in the SoA (Section 1.3).

Page 51 of 133 Version: 10.0 Date: 12 MAY 2021

# 8.2.7 Viral screening (for blood-borne viruses)

The screen will test for: Hepatitis B surface antigen, Hepatitis B core antibody, Hepatitis C antibodies, and HIV-1 and HIV-2 antibodies. For SARS-CoV-2 testing, see Section 8.2.10.

# 8.2.8 Subject diaries

Trial subjects will be given subject diaries at Visit 1 and be asked to record any AEs between visits, solicited local reactions at the injection site (pain, tenderness, erythema/redness, induration/swelling), and solicited systemic reactions (nausea, vomiting, diarrhea, headache, fatigue, myalgia, arthralgia, chills, loss of appetite, malaise, and fever [i.e., ≥38°C]).

Subject diaries may include App-supported electronic documentation in compliance with the applicable data protection regulations.

Trial site personnel will collect subject diaries at the visits given in the SoA (Section 1.3).

#### 8.2.9 Assessment of local reactions

Local reactions after IM immunization will be assessed by the investigator at the times given in the SoA (Section 1.3). This information will be used to validate the solicited assessment of local reactions in the subject diary and potentially support AE reporting.

Local reactions (via daily solicited reports in the subject diaries and as assessed on visit days by the investigator) will be graded based on the guidance given in the US FDA Guidance for Industry "Toxicity Grading Scale for Healthy Adult and Adolescent Volunteers Enrolled in Preventive Vaccine Clinical Trials" for "local reaction to injectable products" (see the section "Assessment of intensity" in Section 10.3.1.11). The reporting of local reactions will be based on the subject's assessments only.

## 8.2.10 SARS-CoV-2 testing

SARS-CoV-2 testing (PCR-based and antibody-based) will be performed at the time points provided in the SoA (Section 1.3).

This includes PCR-based testing for SARS-CoV-2 as an eligibility criterion and blood draws for anti-SARS-CoV-2 antibody testing as baseline reference for immunogenicity analysis.

If required, this reference will allow the discrimination between vaccinated and infected subjects.

The screen for SARS-CoV-2 by PCR-based test using oral swipe sample can be performed by either a central laboratory or a "point of care" device at the trial site.

• If a central laboratory is used: Only the SARS-CoV-2 status will be tested and no further data will be generated.

#### Clinical Trial Protocol Including Amendments Nos. 01 to 04 BNT162-04

Page 52 of 133 Version: 10.0 Date: 12 MAY 2021

• If a point of care device is used: The most commonly used devices come with predefined test panels that test for a range of pathogens and not just for SARS-CoV-2. Thus, inevitably and automatically, incidental data for the pathogens other than SARS-CoV-2 will be generated when using such devices. Since this incidental data is not required by this trial, only the results for SARS-CoV-2 will be recorded in the CRF, analyzed, and reported as described in this protocol. If a test result for SARS-CoV-2 or another pathogen must be reported to relevant authorities, this notification will be done by the trial site.

The anti-SARS-CoV-2 antibody testing will be performed with a commercially available antibody test. In case this commercial antibody test can, discriminate between vaccine-specific and infection-specific antibody responses (based on the antigens used), it will be used to test subjects who may have experienced enhanced respiratory disease or progression of flu-like symptomatology, such as non-resolution of the symptoms after 7 d, symptom kinetics that are inconsistent with a relationship to RNA immunization, as might be expected with a COVID-19 disease (see Section 6.6.3).

In these cases, ad hoc anti-SARS-CoV-2 antibody testing will be performed to test for the development and presence of SARS-CoV-2-specific antibodies, ideally at approximately 14 d and 28 d after the last immunization with the BNT162 candidate vaccine. This data will be used to evaluate the development and progression of an antibody response allowing the diagnosis of a manifest infection.

In case this commercially available test cannot discriminate between vaccine-specific and infection-specific antibody responses, the same kind of analysis will be performed with a custom-made assay specifically developed by the CRO.

## 8.2.11 Subject hotline

Subjects will be provided with contact details for a Subject Hotline, which can be used to contact the trial site during their participation in the trial should they require guidance or should they experience any symptoms of illness. The reporting of any symptoms of illness, e.g., flu-like symptoms, may trigger diagnostic measures (including ad hoc site visits) at the discretion of the investigator. For guidance for specific AEs, see Section 6.6.3.

## 8.2.12 Subject wellbeing questioning

Structured non-leading subject wellbeing questioning will be performed at the time given in the SoA (Section 1.3). Subject responses may trigger more in-depth questioning on specific topics, and may trigger diagnostic measures (including ad hoc site visits) at the discretion of the investigator.

# 8.2.13 Assessment of systemic reactions

Systemic reactions after IM immunization will be assessed via daily solicited reports in the subject diaries and at the times given in the SoA (Section 1.3).

uidance given in US FDA

Page 53 of 133

Version: 10.0

Date: 12 MAY 2021

Systemic reactions will be graded using criteria based on the guidance given in US FDA Guidance for Industry "Toxicity Grading Scale for Healthy Adult and Adolescent Volunteers Enrolled in Preventive Vaccine Clinical Trials" for "systemic reaction grading scale" (see the section "Assessment of intensity" in Section 10.3.1.11).

#### 8.3 Adverse events and serious adverse events

The investigator and any qualified designees are responsible for detecting, documenting, and recording events that meet the definition of an AE or SAE and remain responsible for following up all AEs and SAEs.

# 8.3.1 Time period and frequency for collecting AE and SAE information

All AEs and SAEs will be collected from the date of subject consent until Visit 7; after Visit 7 (at Visits 8 and 9), only IMP-related AEs and SAEs will be collected.

All SAEs (initial and follow-up reports) will be recorded and reported to the sponsor or designee within 24 h after becoming aware of the event, as indicated in Section 10.3.1.10.

Investigators are not obligated to actively seek AEs or SAEs between Visit 9 and Visit 10 and after conclusion of the trial participation. However, if the investigator learns of any SAE, including a death, at any time after a trial subject has been discharged from the trial, and he/she considers the event to be reasonably related to the IMP administration or trial participation, the investigator must promptly notify the sponsor.

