- h) Flexibility for visit days: Visit 3 Day 8±1 d; Visit 4 Day 22±2 d; Visit 5 Day 29±3 d; Visit 5a Day 36±3 d; Visit 6 Day 43±4 d; Visit 7 Day 50±4 d; Visit 8 Day 85±7 d; Visit 9 Day 184±9 d; Visit 10 Day 387±14 d.

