### Clinical Trial Protocol Including Amendments Nos. 01 to 04 BNT162-04

Version: 10.0 Date: 12 MAY 2021

Page 17 of 133

- i) Only for the first 6 subjects per group. Questioning on and documentation of adverse events (AEs) as well as systemic and local reactions, the latter in case of upcoming dose decision meetings.
- j) Only IMP-related AEs and any SAEs except proven COVID-19 cases which have to be reported regardless on severity and relatedness to the trial drug until the last scheduled FU Visit as described into the Section 10.3.1.9.
- k) Blood draw for anti-SARS-CoV-2 antibodies.
- I) For Cohorts 1 and 8, prime immunization with at least 1 h intervals between subjects for the first 6 subjects and then with at least 30 min intervals for the remaining 6 subjects. For all other cohorts, immunization with at least 30 min intervals between subjects.
- m) Oral swipe for SARS-CoV-2 testing either on Day -1 or at the Visit 1 on Day 1.
- n) The listed blood draw days may be adapted if justified by the collected data. Leftover blood after completion of the immunogenicity assessments may be used for additional analyses as described in Section 8.7 (Genetics) and/or Section 8.8 (Biomarkers).
- o) For subjects who have given consent, one aliquot of the blood sample drawn for analysis of CMI may be used for HLA typing to allow additional analysis of T-cell receptor repertoire and/or phenotypic characterization of T cells specific to vaccine encoded antigens.
- p) If HLA typing using the blood sample collected with Lithium Heparin is not conclusive, EDTA-blood will be drawn for HLA testing.
- q) Record any medications that trial subjects receive during the trial in the CRF starting after Visit 0 and until the respective EoT Visit; record any vaccination, including SARS-CoV-2 vaccination that subjects receive, after the EoT Visit until the last FU Visit in the CRF.

Note: If the boost dose is not administered, subjects should still complete all assessments planned in the SoA.

Abbreviations: AE = adverse event; CMI = cell-mediated immune testing; CRF = case report form; D or d = day; ECG = electrocardiogram; EDTA = ethylenediamine tetraacetic acid; EoT = End of Treatment (Visit); FU = follow-up (visit); h = hour(s); HLA = human leukocyte antigen; min = minute(s); Day 0 = one day before Day 1; IMP = investigational medicinal product; min = minute(s); SARS-CoV-2 = the virus leading to COVID-19; WOCBP = women of childbearing potential.

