6.4.3. Adverse events

Definition

For detailed information on adverse events see section 10.3 of the protocol.

AEs will be coded using the Version MedDRA® 23.1 including specific terms for COVID-19 to get a system organ class (SOC) and preferred term (PT) for each AE.

A TEAE is defined as any AE with an onset after the first immunization (if the AE was absent before the first immunization) or worsened after the first immunization (if the AE was present before the first immunization). AEs with an onset date more than 28 days after the last immunization will be considered as treatment emergent only if assessed as related to IMP by the investigator. AEs that cannot be determined to not be treatment emergent due to missing date or time will be defined as TEAE.

Clarification: AEs with an onset date at the date of the first immunization will only be considered as treatment emergent if the AE occurred after the first immunization.

The TEAEs will be evaluated for the following time intervals, clarifying and harmonizing the intervals defined in the protocol:

- Prime immunization up to boost immunization or day 28 (inclusive) after initial immunization (whatever comes first)
- Boost immunization up to day 28 (inclusive) after boost immunization
- All TEAEs (regardless of relationship assessment) occurring from
 - o Prime immunization up to day 28 after boost immunization (inclusive).
 - o If no boost immunization, up to 28 days (inclusive) after prime immunization All TEAEs assessed as related through visit 10.

The intervals starting or ending with an immunization, will start or end with the date and time of the immunization. TEAEs are assigned to the time intervals according to their start date and time.

Adverse events of special interest (AESI)

Enhanced respiratory disease or flu-like symptomatology not resolved after 7 days or with symptom kinetics that are inconsistent with a relationship to RNA immunization will be considered AESIs. AESIs are marked in the CRF.

Analysis

TEAEs with missing time and occurring on the day of prime immunization will be assigned to all intervals starting with the prime immunization. TEAEs with missing time and occurring on the day of the boost immunization will be assigned to all intervals including the boost immunization.

TEAEs with missing date will be assigned to all the respective intervals if it cannot be ruled out, that it belongs to a time interval.

The following TEAE types will be analyzed:

- Any TEAE

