6.5. Secondary Analyses

Hereinafter, the secondary analyses for Part A are described.

Secondary endpoints are functional antibody responses, fold increase in functional antibody titers and the number of subjects with seroconversion. All secondary analyses will be performed using the IMM and possibly additionally the IMMPP population, see section 5.1.

All secondary analysis endpoints will be summarized by group (i.e. by cohort) and all cohorts combined (cohort-total).

The functional antibody response will be assessed at the following time points:

P/B at day 1 (day of primary immunization, pre-dose), 7 ± 1 days and 21 ± 2 days after primary immunization and at 7 ± 3 days, 14 ± 3 days, 21 ± 4 days, 28 ± 4 days, 63 ± 7 days, 162 ± 9 , and 365 ± 14 days after the boost immunization.

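### All-AE collection ends at Visit 7, which can fall 22 d after boost, so the 28 d post-boost window of the primary TEAE endpoint is not guaranteed for subjects with an early Visit 7

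*Protocol*

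**What the plan says.** **Endpoint.** Protocol section 3 and SAP 1.1 define the third primary endpoint as the proportion of subjects with at least one unsolicited TEAE, in a post-prime period and up to 28 d after boost. SAP 6.4.3 sets the second interval as "Boost immunization up to day 28 (inclusive) after boost immunization". Under protocol 10.3.1, relatedness decides treatment emergence only for onsets more than 28 d after the last dose. Inside 28 d, unrelated AEs count.

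**Collection.** Protocol 8.3.1 states "All AEs and SAEs will be collected from the date of subject consent until Visit 7" and continues "after Visit 7 (at Visits 8 and 9), only IMP-related AEs and SAEs will be collected". Footnote j of the schedule of activities gives the rule for Visits 8 to 10 as "Only IMP-related AEs and any SAEs except proven COVID-19 cases which have to be reported regardless on severity and relatedness to the trial drug". Proven COVID-19 therefore stays reportable after Visit 7.

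**Timing.** Footnote h of the schedule gives the boost visit as "Visit 4 Day 22±2 d" and the end-of-treatment visit as "Visit 7 Day 50±4 d". The column heading places Visit 7 about 28 d from Visit 4. SAP 6.5 counts the later immunogenicity visits from boost, including "28 ± 4 days, 63 ± 7 days". Neither document requires Visit 7 to be at least 28 d after the actual boost date.

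**Denominator.** SAP 6.1.1 uses the number of subjects in the analysis set unless stated otherwise. SAP 6.1.3 does not substitute missing data. SAP 6.4.3 adds no rule for incomplete follow-up.

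**The concern.** The endpoint needs every AE for 28 d after boost, but collection of every AE is tied to a visit with its own window, not to day 28. If Visit 7 is early, the last days of the interval are observed only for related AEs, SAEs and proven COVID-19. The subject is still counted as if all 28 days had been seen.

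The error can go in one direction only. Missed events leave the numerator and the denominator does not change. A late Visit 7 elsewhere does not compensate, because the interval closes at day 28. The SAP's cumulative interval (all TEAEs regardless of relationship, from prime to day 28 after boost) has the same gap.

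For other endpoints the SAP ties the denominator to what was observed. Solicited reactions use subjects with diary information in the interval (6.4.1), and seroconversion uses subjects with data at the visit (6.5.3). The TEAE proportion has no such rule and no disclosure of follow-up. Repeating AE analyses in the safety boost set removes unboosted subjects but does nothing for a boosted subject with an early Visit 7.

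**Working it through.** **The plan's own figure.** Protocol 9.2 and SAP section 4 give 85.8% as the chance of seeing a TEAE of 15% incidence at least once in 12 subjects. 1 − 0.85^12 = 0.8578. This is reproduced and is not in dispute.

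**Interval from boost to Visit 7**
- Boost window: Day 20 to Day 24. Visit 7 window: Day 46 to Day 54.
- Shortest: 46 − 24 = 22 d, leaving days 23 to 28 (6 d) uncovered.
- Nominal: 50 − 22 = 28 d, nothing uncovered.
- Longest: 54 − 20 = 34 d.
- Counted from boost as 28 ± 4 d: shortest 24 d, up to 4 d uncovered.

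**How often it is short.** The documents give no actual visit dates. Assume every day in each window is equally likely and the two visits are independent, giving 5 × 9 = 45 day pairs.

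| Days from boost to Visit 7 | 22 | 23 | 24 | 25 | 26 | 27 |
|---|---|---|---|---|---|---|
| Pairs | 1 | 2 | 3 | 4 | 5 | 5 |
| Days lost per pair | 6 | 5 | 4 | 3 | 2 | 1 |

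- Short pairs: 20 of 45 = 44%. The other 25 (56%) cover the full window.
- Total shortfall: 6 + 10 + 12 + 12 + 10 + 5 = 55 d. Mean 55/45 = 1.22 d overall, and 55/20 = 2.75 d among short pairs.
- With 28 ± 4 d counted from boost: 4 of 9 days short (44%), mean 10/9 = 1.11 d.

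**Effect on the proportion.** Assume a constant hazard and, as the least favourable case, that every event in the gap goes unrecorded. If P is the true 28 d proportion and d the days observed (at most 28), the observed proportion is 1 − (1 − P)^(d/28). The values of P are an assumed range.

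| True 28 d proportion | Uniform visit days | Everyone at 24 d | Everyone at 22 d |
|---|---|---|---|
| 15% | 14.4% | 13.0% | 12.0% |
| 30% | 28.9% | 26.3% | 24.4% |
| 50% | 48.4% | 44.8% | 42.0% |

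The loss is 0.6 to 1.6 points with uniform visit days and 3.0 to 8.0 points with everyone at 22 d. In a cohort of 12, 0.6 to 1.6 points is 0.07 to 0.19 of a subject.

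If only half the events are unrelated, non-serious and not COVID-19, half the hazard in the last 6 d is still captured and the exponent at 22 d becomes (22 + 3)/28. The observed values are then 13.5%, 27.3% and 46.1%.

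**Effect on the detection probability at 15%.** With uniform visit days: 1 − (1 − 0.144)^12 = 84.5%. With everyone at 22 d: 1 − (1 − 0.120)^12 = 78.4%. The plan states 85.8%.

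**The case against.** **The nominal schedule covers the window.** Correct. The defect is the absence of a guarantee for early visits, not a shortfall for everyone. A reader might infer that the 28 d window is generally unobserved. The documents do not support that.

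**22 d is the extreme.** Also correct. Counting from boost gives 24 d. The gap remains, at up to 4 d instead of 6.

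**Few events are affected.** Related AEs, SAEs and proven COVID-19 are still captured. A lost AE changes the primary proportion only if it was the subject's first unsolicited TEAE in the interval. This stands and makes the figures above upper-end for each timing scenario.

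**The events may exist in source.** Diaries are issued at Visit 7 and collected at Visit 8, and protocol 8.2.8 asks subjects to note any AEs between visits. A reader might infer that gap events are lost for good. That goes too far, but nothing requires an unrelated, non-serious entry to be carried into the CRF.

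**The effect is negligible and no test depends on it.** The trial is descriptive, and the expected loss is under a fifth of a subject per cohort. That limits severity. It does not justify labelling a primary proportion as 28 d without saying who was followed for 28 d. One subject in 12 is 8.3 points, so a missed event shows if it happens, though on these assumptions it seldom would.

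**The protocol change comes too late.** This largely stands. Protocol 10.0, dated 12 May 2021, says vaccinations were complete as of 12 March 2021. Adding the longest in-window gap of 34 d puts the last on-schedule Visit 7 at 15 April 2021. The last on-schedule Visit 8 is at most 92 − 20 = 72 d after boost, by 23 May 2021.

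**Conclusion.** The mismatch between collection and endpoint is real, and neither document closes it. Full 28 d observation after boost is not assured for subjects whose Visit 7 is early, and any resulting bias in the primary TEAE proportion is downward.

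The likely size is about 0.6 to 1.6 points for true proportions of 15% to 50%. This rests on uniform independent visit days, a constant hazard and loss of every gap event, none of which is in the documents. About 3 to 8 points is the ceiling, with every subject at 22 d. The 22 d and 24 d minima come straight from the stated windows.

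A reader might also infer that the bias differs between cohorts and so distorts the dose comparison. That is possible only if visit timing differed by cohort, and the documents hold no visit-timing data. The point is a modest one about follow-up and disclosure. It does not invalidate the endpoint.

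**What to change.** **SAP 6.4.3 (the change that matters).**
- Report, per cohort, the number of boosted subjects with less than 28 d of all-AE follow-up after boost. This needs only the boost and Visit 7 dates.
- Add a sensitivity table for the post-boost interval that accounts for the shortfall. It could be restricted to a post-boost period that all subjects completed (22 d, if all visits were in window) or to subjects with the full 28 d.
- Use AEs noted in diaries between Visit 7 and Visit 8 where available.
- Footnote the main table to say that all-AE collection ended at Visit 7.

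**Protocol 8.3.1 (consistency).** Collect all AEs until Visit 7 or 28 d after the last immunization, whichever is later, and align footnote j of the schedule. For most or all subjects this can no longer change what was collected.

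**Cost.** One extra table, one count per cohort and a footnote; no extra visit. The sensitivity table uses slightly less data than the main table, so it should sit beside the main table and not replace it.

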# 8.3.2 Method of detecting AEs and SAEs

The method of recording, evaluating, and assessing causality of AEs and SAEs and the procedures for completing and transmitting SAE reports are provided in Section 10.3.

Care will be taken not to introduce bias when detecting AEs and/or SAEs. Open-ended and non-leading verbal questioning of the trial subject is the preferred method to inquire about AE occurrences.

